6.1 Fasting Lipid Profile Analyses

6.1.1 Fasting Lipid Profile Analyses in Part A

A fasting lipid profile will be collected from all subjects in each dosing period in Part A, except for dosing period 4 for Cohort 2 which prescribes dosing subjects in a fed state. Fasting measurements of TG, TC, and HDL-c will be obtained and fasting measurements of LDL-c and non-HDL-c will be derived from plasma samples collected just prior to dosing on the day of dosing, then at 24, 48 and 96 hours after dosing.

A last observation measurement will be derived for each subject using the last post-dose measurement of a lipid parameter. Change from baseline for each of the lipid parameters will be derived for each of the post-dosing time points (Day 1 [24 hours], Day 2 [48 hours], and Day 4 [96 hours]) and the last observation using the pre-dose measurement from the day of dosing as the baseline.

Descriptive statistics for the measurement at baseline and the measurement and change from baseline at each post-dose time point plus the last observation will be tabulated.

A mixed-effect repeated measures (MMRM) analyses will be conducted for each lipid parameter using the change from baseline values from Days 1, 2, and 4. The MMRM model for change from baseline will contain fixed effects for treatment, time, and their interaction, a random effect for subject, and the baseline measurement as a covariate. The covariance structure among the repeated measurements for a subject will be assumed to be common across subjects and modeled using an unstructured 3x3 matrix. Satterthwaite's approximation will be used to estimate denominator degrees of freedom. Any missing assessments will be assumed to be missing at random, so estimates of treatment effects from the model will be assumed to be unbiased. These analyses will be performed using the SAS procedure PROC MIXED. The tabular output for these MMRM analyses will present the least squares means, standard errors and 95% confidence intervals and Type 3 p-values for each main effect marginal. Pairwise contrasts of the least squares means between the LY dose levels and placebo along with the associated 95% confidence interval and Type 3 p-values will also be provided at each time point using LSMESTIMATE statements.

Plots of the least squares mean \pm standard error estimates for each lipid parameter over time (pre-dose through Day 4 post-dose) will be provided by treatment group.

A last observation analysis will be performed for change from baseline using an analysis of covariance (ANCOVA) model with a fixed effect for treatment a random effect for subject and the baseline value as a covariate. Tabular output for these ANCOVA analyses will present the least squares means, standard errors and 90% confidence intervals and Type 3 p-values for each main effect marginal. Pairwise contrasts of the least squares means between each LY dose level and placebo along with the associated 95% confidence interval and Type 3 p-values will also be provided.

6.1.2 Fasting Lipid Profile Analyses in Part B

Fasting lipid profiles will be collected from all subjects in Part B just prior to dosing on the day of dosing, Day 7, Day 14, Day 21, and Day 28, and 7 (Day 35) days after stopping dosing of the randomized treatment. An additional follow-up assessment will be collected 14 (Day42) or 28 (Day 56) days after stopping dosing of the randomized treatment for Cohort 3 (5mg QD) and Cohorts 4 through 6, respectively.

A last on-treatment observation measurement will be derived for each subject using the last post-dose measurement for a lipid parameter taken while the subject is taking study medication during the 28-day treatment period. Change from baseline for each of the lipid parameters will be derived for each of the post-dosing time points (Days 7, 14, 21, 28, 35, and 42 or 56) and the last on-treatment observation using the pre-dose measurement from the first day of dosing as the baseline.

Descriptive statistics for the measurement at baseline and the measurement and change from baseline at each post-baseline time point plus the last observation will be tabulated.

An MMRM analysis will be conducted for each lipid parameter using the change from baseline values from Days 7, 14, 21, 28, 35, and 42. The MMRM model for change from baseline will contain fixed effects for treatment, time, and their interaction, a random effect for subject, and the baseline measurement as a covariate. Since the time points are evenly spaced the covariance structure among the repeated measurements for a subject will be assumed to be common across subjects and modeled using a autoregressive(1) 7x7 matrix. Satterthwaite's approximation will be used to estimate denominator degrees of freedom. Any missing assessments will be assumed to be missing at random, so estimates of treatment effects from the model will be unbiased.

These analyses will be performed using the SAS procedure PROC MIXED. The tabular output for these MMRM analyses will present the least squares means, standard errors and 95% confidence intervals and Type 3 p-values for each main effect marginal. Pairwise contrasts of the least squares means between the LY dose levels and placebo along with the associated 95% confidence interval and Type 3 p-values will also be provided at each time point using LSMESTIMATE statements.

Plots of the least squares mean \pm standard error estimates for each lipid parameter over time (baseline through Day 56) will be provided by treatment group.

A last on-treatment observation analysis will be performed for change from baseline using an analysis of covariance (ANCOVA) model with a fixed effect for treatment a random effect for subject and the baseline value as a covariate. Tabular output for these ANCOVA analyses will present the least squares means, standard errors and 95% confidence intervals and Type 3 p-values for each main effect marginal. Pairwise contrasts of the least squares means between each

LY dose level and placebo along with the associated 95% confidence interval and Type 3 p-values will also be provided.

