10.6. Pharmacodynamics

Pharmacodynamic blood samples of approximately 10 mL will be collected in Parts A and B as specified in the Schedule of Events ([Appendix 2](#)).

Plasma TG, TC, and high-density lipoprotein cholesterol (HDL-c) (to calculate LDL-c and non-HDL-c) will be assessed in the fasted state for the first 4 hours postdose and then again during the post-prandial period following a high-fat meal administration at 4 hours postdose in Part B. Changes in these PD markers from baseline (Day -1) and Day 28 will be assessed at each dose level to find at least 1 dose level that shows evidence of target engagement by a decrease in fasting or post-prandial lipids.

The lipid lowering ability of LY3202328 in subjects with a statin-free background will be quantified by TG, TC, and HDL-c (to calculate LDL-c and non-HDL-c) in Parts A and B, and by LDL-c ultracentrifugation methods in Part B only.

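### SAP 6.1.2: the Part B fasting-lipid MMRM cannot be run as written (visit list, matrix size, spacing reason, baseline), but the contrasts at Days 7 to 35 are estimable under every reading

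*SAP*

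**What the plan says.** **Visits collected.** After Day 35, SAP 6.1.2 states: "An additional follow-up assessment will be collected 14 (Day42) or 28 (Day 56) days after stopping dosing of the randomized treatment for Cohort 3" and Cohorts 4 through 6, respectively. Day 42 therefore belongs to Cohort 3 (5 mg) and Day 56 to Cohorts 4 to 6 (20, 100 and 300 mg). Protocol 6.1.2 gives follow-up visits on Days 35 and 56 and mentions no Day 42.

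**Visits analysed.** Change from baseline is derived at "Days 7, 14, 21, 28, 35, and 42 or 56". The MMRM is then fitted "using the change from baseline values from Days 7, 14, 21, 28, 35, and 42", without Day 56. Yet the LS-mean plots are to show "estimates for each lipid parameter over time (baseline through Day 56) will be provided by treatment group".

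**Covariance.** The stated reason begins "Since the time points are evenly spaced the covariance structure among the repeated measurements", and the structure is "modeled using a autoregressive(1) 7x7 matrix". SAP 6.3 repeats the even-spacing reason for the exploratory biomarkers.

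**Output.** LS means for each main-effect marginal, and LY-placebo contrasts at each time point.

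**Baseline.** SAP 6.1.2 derives change "using the pre-dose measurement from the first day of dosing as the baseline". Protocol 10.6 says of the same lipids: "Changes in these PD markers from baseline (Day -1) and Day 28 will be assessed at each dose level". SAP 6.3 also uses Day -1.

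**Population.** SAP 2.2.1 limits the PD Population to subjects with at least one dose of LY. SAP 2.2.2 lists Placebo as a Part B treatment group.

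**The concern.** A programmer cannot follow every sentence of SAP 6.1.2 at once. The choice made decides which planned table rows exist and what the final follow-up contrast compares. The visit list, the matrix size, the spacing reason and the plot range do not agree with one another or with the collection scheme.

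The baseline is a separate matter and reaches further, because it enters every change score, the MMRM covariate and the ANCOVA, including the Day 28 comparison. Fasting lipids are a secondary objective. Protocol 11.3.4 has unblinded sponsor staff evaluate Part B lipids after the 20, 100 and 300 mg levels, so these choices are better fixed in the SAP than made later.

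**Working it through.** **Inputs.** Four cohorts of 8 LY + 2 placebo (SAP 1.3); five treatment groups with placebo pooled over cohorts (SAP 2.2.2); fixed effects for treatment, time, treatment-by-time and baseline (SAP 6.1.2); collection days as above.

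**The plan's own figure.** Days 7, 14, 21, 28, 35 and 42 are six levels, hence 6x6. The stated 7x7 is not reproduced, and this would be so even if every cohort had Day 42.

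**Estimability.** With treatment-by-time in the model, each treatment-day cell has its own parameter. A cell with no data is not estimable, nor is any marginal that weights it. As listed there are 40 x 5 + 10 = 210 records. Day 42 holds 8 subjects on 5 mg, 2 on placebo and none on 20, 100 or 300 mg. A rank test was used: a row is estimable if adding it to the design matrix leaves the rank unchanged.

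| Reading | Levels | Gaps (days) | Contrasts estimable | LY marginals not estimable |
|---|---|---|---|---|
| Days 7-42 as listed | 6 | 7 throughout | 21 of 24 | 20, 100, 300 mg |
| 42 or 56 pooled | 6 | last is 7 (Cohort 3) or 21 (Cohorts 4-6) | 24 of 24 | none |
| 42 and 56 separate | 7 | last is 14 | 24 of 28 | all four |
| Days 7-35 only | 5 | 7 throughout | 20 of 20 | none |

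The failures are Day 42 for 20, 100 and 300 mg, plus Day 56 for 5 mg when the days are separate. As listed, the Day 42 time marginal also fails, and there is no Day 56 LS mean to plot.

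Counting baseline as the seventh level does not rescue the text. Its change is identically zero. With the listed days the same three Day 42 contrasts fail, and with the pooled visit the last gap is still uneven.

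**Cost of the pooled reading.**
- Comparability: 5 mg at Day 42 is compared with placebo measured at Day 42 in 2 subjects and at Day 56 in 6.
- Spacing: the documents give no within-subject correlation, so assume that it decays with actual time, with a 7-day correlation r of 0.5, 0.7 or 0.9. The 21-day correlation between Days 35 and 56 is r^3 = 0.125, 0.343 or 0.729. AR(1) by visit order, fitted to the mixture of 10 subjects ending at Day 42 and 30 ending at Day 56, gives 0.444, 0.646 or 0.874 for that pair.
- Variance: the calculation assumes complete data and a between-subject share of variance of 0, 0.3 or 0.5. Model-based variance of a by-visit contrast is off by at most 0.2%. For the six-visit treatment marginal that the SAP plans, the LY-placebo variance is understated by about 0.2-1.0% for 20, 100 and 300 mg and by 1.5-6% for 5 mg. The worst case is about 3% in the standard error (square root of 0.94 = 0.97).

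**SAP 6.3.** ApoC3, PCSK9, Lp(a) and insulin are taken after baseline on Days 14, 28, 35, and 42 or 56. The gaps are 14, 7, and 7 or 21 days, so the even-spacing reason is false on any reading.

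**Baseline.** SAP 6.1.2 names Day 1 pre-dose; Protocol 10.6 and SAP 6.3 name Day -1. The Part B schedule appears to show no Day 1 lipid draw, but that table was machine-read, so this is supporting evidence only. The conflict in the text stands without it. No size can be given, because the documents state no lipid variability.

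**Population.** Part B is parallel-group, so its 4 x 2 = 8 placebo subjects never receive LY. Under SAP 2.2.1 as worded, all 8 fall outside the PD Population, and no LY-placebo contrast could be formed.

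**The case against.** The likeliest explanation is that the words for Day 56 were dropped from the MMRM sentence. The same section uses the pooled form when deriving changes, and SAP 6.3, 7.3.2, 7.4.3 and 7.5.2 treat Day 42 or 56 as one final visit. Under that reading every planned contrast and marginal is estimable, and the numerical cost of the spacing error is small. The non-estimability under the other readings gives blank rows, which are noticed when the program runs, rather than biased estimates. This stands, and it limits the point to a correction of wording and covariance structure.

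On baseline, Protocol 10.6 mainly describes the serial profile on Days -1 and 28, and a Day 1 pre-dose baseline would be defensible if such a draw exists. But that section names fasting lipids and a Day -1 baseline, so the SAP should say which applies.

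A reader might infer more than the documents support:
- That the Day 42/56 split explains the 7x7. It does not; the count error is separate.
- That the spacing error understates variance by 2-8%. That range is for a Days 7-28 mean, which the SAP does not plan.
- That the interim lipid reviews turn on the visit coding. Protocol 11.3.4 does not link them.
- That placebo subjects are meant to be excluded. SAP 2.2.2 and the planned contrasts show otherwise.

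**Conclusion.** The point holds in limited form. SAP 6.1.2 contains a count error (six days against 7x7), a visit list that leaves Day 42 empty for three of four doses, a plot range beyond the modelled days, and a baseline at odds with Protocol 10.6 and SAP 6.3. Under the favoured pooled reading everything is estimable, but the reason given for AR(1) fails and the final level mixes days. The spacing reason is also false for four biomarkers in SAP 6.3, and the PD Population wording omits Part B placebo subjects.

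It would be wrong to conclude that the lipid analysis as a whole fails. Once placebo is included, all 20 contrasts at Days 7 to 35, including Day 28, are estimable under every reading, and visit coding does not touch the last on-treatment ANCOVA. These are secondary endpoints in a study that Protocol 11.1 says is not powered. Only the baseline choice and the population wording reach the Day 28 result, and the effect of the baseline choice cannot be sized from the documents. The variance figures rest on the assumed correlations and complete data; the estimability counts rest only on the stated design with all planned visits attended.

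**What to change.** 1. **Baseline.** Use the Day -1 Hour 0 fasting sample for the MMRM and the ANCOVA in SAP 6.1.2, in line with Protocol 10.6, after checking in the original schedule whether a Day 1 lipid draw exists.
2. **MMRM.** Either fit the days common to all cohorts (7, 14, 21, 28, 35) with a 5x5 AR(1) matrix and describe the final follow-up by actual day, ending the LS-mean plots at Day 35; or keep Day 42 or 56 as one labelled final level, use a spatial-power structure on actual study day, and footnote the mixed days. Apply the same choice to FFA, beta-hydroxybutyrate and ApoB100 in SAP 6.3.
3. **Sparse biomarkers (SAP 6.3).** For ApoC3, PCSK9, Lp(a) and insulin, replace AR(1) by visit order with spatial power on actual day, or with an unstructured matrix without the random subject effect, which would be redundant.
4. **PD Population (SAP 2.2.1).** Require at least one dose of LY or placebo.
5. **Follow-up day.** Reconcile the SAP's Day 42 with the protocol's Day 56.

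An on-drug treatment marginal over Days 7 to 28 is optional; it would change what is estimated rather than correct an error.

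The cost is mainly SAP wording. The first option in item 2 gives up the model-based estimate at the final follow-up visit; the second keeps it, but compares mixed days.

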1.3 Study Design with Sample Size Justification

Study I8Q-MC-GSEA(a) (GSEA) is a first-in-man, Phase 1, randomized, double-blind, placebo-controlled, 2-part, ascending single- and multiple-oral dose study of LY in overweight, healthy subjects (Part A) and in dyslipidemic, statin-free, overweight, healthy subjects with a statin drug-drug interaction (DDI) assessments (Part B).

This study will be conducted in 2 parts: Part A, a single ascending dose (SAD) study design at a single site and Part B, a multiple ascending dose (MAD) study design conducted in multiple sites.

Eighteen statin-free, overweight, healthy males and female subjects may be enrolled in one of two 9-subject cohorts in Part A. Each subject is scheduled to receive 2 single doses of LY and 1 dose of placebo in ascending dose levels. This sample size is customary for Phase 1 studies evaluating safety, tolerability, and pharmacokinetic parameters, and is not powered on the basis of statistical hypothesis testing.

Forty statin-free, overweight, dyslipidemic subjects may be enrolled in Part B. Subjects will be enrolled in one of four dose-ascending 10-subject cohorts (8 subjects will receive LY and 2 subjects will receive placebo in each cohort). This sample size is a customary sample size for a Phase 1b MAD study evaluating safety, tolerability, and pharmacokinetic parameters.

2 General Statistical Methodology and Conventions

Chorus will designate a provider to generate the statistical analyses detailed in this SAP. All computations for statistical analyses will be performed using SAS® software, Version 9.3 or later. All SAS programs used in the production of statistical summary outputs will be validated with independent programming prior to finalization. In addition, all program outputs will be independently reviewed. The validation process will be used to confirm that all data manipulations and calculations were accurately done. Once validation is complete, a senior statistical reviewer will perform a final review of the documents to ensure the accuracy and consistency with this plan and consistency within tables. Upon completion of validation and quality review procedures, all documentation will be collected and filed by the project statistician or designee.

For the implementation of parametric methods of analysis, residual plots will be examined to determine if model assumptions are satisfied. Transformations or nonparametric methods of

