6.2.2 Post-prandial Lipid Profile Analyses in Part B

Measurement of the lipids TC, TG, HDL-c, LDL-c, and non-HDL-c will be obtained just prior to the midday meal on Days -1 and 28 of dosing. Post-meal measurements will be collected on both days at 0.5, 1, 2, and 4 hours after the meal for all subjects in Part B.

Change from baseline for each of the lipid parameters will be derived for each of the post-meal time points using the pre-meal measurement as the baseline, and the level of excursion within the 4-hour post-meal period will be determined using the post-meal AUC, as described in Section 6.2.1.

Descriptive statistics for the post-meal AUC at Days -1 and 28 as well as the difference between Days -1 and 28 will be presented by treatment group.

An ANCOVA will be conducted for each lipid parameter using the difference in post-meal AUC values from Day -1 to Day 28. The ANCOVA model will have a fixed effect for treatment, a random effect for subject, and the Day -1 post-meal AUC as a covariate.

Boxplots of the lipid values at pre-meal and each planned post-meal time point (0.5, 1, 2, and 4 hours post-meal) will be presented for each treatment group for both Day -1 and Day 28.

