6.3 Exploratory Biomarkers

The exploratory biomarkers FFA, β -hydroxybutyrate, and ApoB100 will be assessed from samples collected from all subjects in Part B on Day -1, Day 7, Day 14, Day 21, and Day 28,

plus 7 (Day 35) and 14 (Day 42) or 28 (Day 56) days after stopping dosing of the randomized treatment, while the biomarkers ApoC3, PCSK9, Lp(a) and insulin will only be collected on Day -1, Day 14, Day 28, Day 35, and Day 42 or 56. While the subjects are receiving randomized study medication samples will be collected just prior to dosing.

For each parameter a last on-treatment observation measurement will be derived for each subject using the last post-dose measurement for a parameter taken while the subject is taking study medication during the 28-day treatment period. Change from baseline for each parameter will be derived for each of the post-dosing time points (Days 7, 14, 21, 28, 35, and 42 or 56) and the last on-treatment observation using the Day -1 measurement as the baseline.

Descriptive statistics for the measurement at baseline and the measurement and change from baseline at each post-baseline time point plus the last observation will be tabulated.

An MMRM analysis will be conducted for each parameter using the change from baseline values. The MMRM model for change from baseline will contain fixed effects for treatment, time, and their interaction, a random effect for subject, and the baseline measurement as a covariate. Since the time points are evenly spaced the covariance structure among the repeated measurements for a subject will be assumed to be common across subjects and modeled using an autoregressive matrix. The analyses will be conducted and tabulated as described in Section 6.1.2.

Plots of the least squares mean \pm standard error estimates for each parameter over time (baseline through Day 56) will be provided by treatment group.

A last on-treatment observation analysis will be performed for change from baseline using an ANCOVA model with a fixed effect for treatment, a random effect for subject and the baseline value as a covariate. The analyses will be conducted and tabulated as described in Section 6.1.2.

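### The three Part B ANCOVAs carry a random subject effect with only one record per subject, so the term cannot be estimated and the SAP leaves their degrees of freedom undetermined

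*SAP*

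**What the plan says.** Three Part B analyses are described as ANCOVA with a random subject effect.

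- **SAP 6.1.2, last on-treatment fasting lipids.** The model has "a fixed effect for treatment a random effect for subject and the baseline value as a covariate". The response is one value per subject: "A last on-treatment observation measurement will be derived for each subject using the last post-dose measurement". Planned output is least squares means, standard errors, 95% confidence intervals and p-values, with contrasts of each LY dose against placebo.
- **SAP 6.2.2, post-prandial lipids.** The analysis is run "using the difference in post-meal AUC values from Day -1 to Day 28", again one number per subject, with "a random effect for subject, and the Day -1 post-meal AUC as a covariate". No p-values or intervals are listed for this model.
- **SAP 6.3, biomarkers.** The last on-treatment value is analysed by an "ANCOVA model with a fixed effect for treatment, a random effect for subject and the baseline value as a covariate", conducted and tabulated as in 6.1.2.

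Satterthwaite degrees of freedom are named in 6.1.2 only in the MMRM paragraph. No rule is given for the ANCOVAs. Protocol 11.3.3 makes ANCOVA with baseline as a covariate the default for endpoints measured only at baseline and end of therapy, and mentions no subject effect.

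**The concern.** A random subject effect describes correlation among several records from the same person. Part A has such records: each subject is dosed in at least three periods, and the last-observation ANCOVA in SAP 6.1.1 rightly includes the term. The model sentence in 6.1.2 matches the one in 6.1.1 and appears to have been carried across. In these Part B analyses nothing repeats within a subject, so the subject effect and the residual are the same quantity under two names.

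At stake is whether the text defines a single analysis. A confidence interval or p-value needs a reference distribution as well as an estimate and a standard error. If the model contains a term that cannot be estimated and no degrees-of-freedom rule is given, the output depends on how the software handles the fit. SAP section 2 calls for validation by independent programming, and two programmers following this text could obtain different intervals, or one could obtain none.

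**Working it through.** The plan states no degrees of freedom for these models, so there is no figure to reproduce first.

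**Inputs.** "Forty statin-free, overweight, dyslipidemic subjects may be enrolled in Part B" (SAP 1.3), in four cohorts of 8 LY and 2 placebo: 4 × 8 = 32 LY and 4 × 2 = 8 placebo, N = 40. There are five treatment groups (SAP 2.2.2), one baseline covariate, and one record per subject.

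**Step 1: variance structure.** Let X be the fixed-effects design and Z the subject design. With one record per subject, Z = I, so

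V = σ²(subject)·I + σ²(residual)·I = [σ²(subject) + σ²(residual)]·I.

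Only the sum is identifiable.

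**Step 2: counting degrees of freedom.**

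| | Stated design | PD Population read literally |
|---|---|---|
| N, groups | 40, 5 | 32, 4 |
| rank X = groups + 1 | 6 | 5 |
| rank [X Z] | 40 | 32 |
| N − rank [X Z] | 0 | 0 |
| N − rank X (ordinary ANCOVA) | 34 | 27 |

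The right-hand column arises because SAP 2.2.1 requires at least one dose of LY for the PD Population, which read literally removes the Part B placebo subjects.

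**Step 3: what stays fixed and what does not.** One illustrative data set was simulated (assumed values: baseline mean 250 and SD 70, residual SD 50, 8 per group). The subject share of total variance was fixed at 0, 0.25, 0.5, 0.75 and 0.99. At every share, the REML log-likelihood was −151.1167 and the contrast of the highest dose group with placebo was −26.25, with SE 18.59 and t = −1.41.

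A fitted random-intercept model divided the variance arbitrarily, 691.03 + 691.03 = 1382.06, which is the ordinary ANCOVA residual variance. It gave a standard error of about 6.7 × 10⁷ for the subject variance. Its fixed effects and standard errors equalled ordinary least squares. Its p-value for the contrast was 0.158 (normal reference), against 0.167 on 34 df.

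**Step 4: Satterthwaite, if borrowed from the MMRM paragraph.** With Z = I, every entry of the 2 × 2 REML information matrix for the two variances is 34/(2σ⁴) = 17/σ⁴, where σ² is the total variance. The determinant is 0, so there is no ordinary inverse. The Moore–Penrose inverse has every entry σ⁴/(4 × 17) = σ⁴/68. A contrast variance cσ² has gradient (c, c), so its estimated variance is 4c²σ⁴/68 = c²σ⁴/17, and

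df = 2(cσ²)² / (c²σ⁴/17) = 34.

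Satterthwaite therefore gives 34, but only if the software uses a generalised inverse.

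**Step 5: after deleting the term.** With 34 df the critical value is t = 2.032. For 8 against 8 with balanced baseline, the 95% half-width is 2.032 × √(2/8) = 1.02 residual SD. With 27 df it is 2.052 × 0.5 = 1.03 residual SD, for a dose-against-dose contrast.

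**The case against.** The strongest reply is that the term is redundant and does no harm. The contrasts, standard errors and t statistics need only the total variance, which is identified. The stated model can be fitted and can return p-values close to the ordinary ANCOVA ones. Zero degrees of freedom belongs to one counting rule, which the SAP does not name. Protocol 11.3.3 already gives the workable model, and SAP section 2 provides for program validation, senior statistical review, and changes of method documented in the CSR. A singular-fit warning would probably be caught there.

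Most of this stands, and it rules out two stronger readings. A reader might infer that the model cannot produce the planned p-values and intervals, or that its error term is undefined. Steps 3 and 4 show otherwise: failure arises only under a rule that subtracts the subject effects as well. A reader might also infer that the secondary objective on fasting lipids goes unanswered. The documents do not support that. SAP 2.3 names MMRM for the PD endpoints, and the Part B MMRM has repeated records per subject, so it is untouched by this point. Sections 6.2.2 and 6.3 serve exploratory objectives, and protocol 11.1 says Part B is not powered for hypothesis testing.

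The reply does not supply the missing rule. The SAP still specifies a term that cannot be estimated and does not say which degrees of freedom apply. Leaving this to validation means explaining a change of model in the CSR that could have been settled in the plan.

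**Conclusion.** The point holds as a specification error of low severity. In the Part B ANCOVAs of SAP 6.1.2, 6.2.2 and 6.3, subject variance is fully confounded with residual variance. Estimates and standard errors equal those of ordinary ANCOVA. The reference degrees of freedom are not determined by the SAP: 0 under a residual rule that counts subject effects, 34 under ordinary ANCOVA. In the simulated example, the gap between a normal reference and 34 df was 0.158 against 0.167.

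The consequence for planned p-values and intervals applies to 6.1.2 and, by cross-reference, 6.3; 6.2.2 does not expressly plan them. The 34 assumes that all 40 subjects contribute a value and that placebo is pooled across cohorts as a fifth group. It becomes 27 under the literal PD Population. That reading would also remove the planned placebo contrasts, which is a separate matter. Dropouts or replacements would change N, but not the confounding.

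**What to change.** Delete the random subject effect from the Part B ANCOVAs in SAP 6.1.2, 6.2.2 and 6.3. This leaves treatment as a fixed effect and the baseline value (in 6.2.2, the Day −1 AUC) as the covariate, in line with the default in protocol 11.3.3. Degrees of freedom then follow as N − groups − 1, which is 40 − 5 − 1 = 34 as designed. Keep the term in the Part A analyses, where subjects contribute several periods. The Part B MMRM needs no change on this account.

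The cost is three deletions. No data collection, design feature, treatment estimate or standard error changes.
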